8.2.1. Inclusion Criteria

Patients must meet all the following inclusion criteria to be eligible for inclusion in the study:

1. Diagnosed RA patients.
2. ≥ 18 years of age.
3. Did not receive previous another biological treatment.

8.2.2. Exclusion Criteria

Patients meeting any of the following criteria will not be included in the study:

1. Had previous biological treatment.
2. Use of etanercept for less than 1 year.

8.3. Data Sources

Patients will be identified from the rheumatology patient registry with rheumatoid arthritis and obtained information on patient demographics (age, gender), education level (years), present smoking status, disease duration (years), current MTX and steroid therapy (yes/no), baseline Disease Activity Score 28(DAS28) and Clinical Disease Activity Index (CDAI), RF status, anti-CCP status. Primary Outcomes: DAS28 and CDAI in last follow-up visit.

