8.2. Setting

Patients and Methods

Data will be collected from the Baghdad Teaching Hospital registry. The rheumatology patient registry is a prospective longitudinal multicenter cohort initiated in 2012. It captures all patients treated with biologic therapies managed in the rheumatology department. The decision to initiate and maintain the treatment is guided by the American College of Rheumatology (ACR) recommendations.

Study population

Patients will be included in the study if they meet the American College of Rheumatology/The European League Against Rheumatism (EULAR) 2010 criteria for Rheumatoid Arthritis,⁵ with at least 1 year of follow-up after starting their first biologic therapy. This includes patients who were in monotherapy or in combo-therapy with concomitant conventional DMARDs.

Hypothesis

Our hypothesis is that there is no difference in response between seropositive and seronegative RA patients to Enbrel.

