8.6. Data Analysis

Categorical covariates will be described by frequency distribution while continuous covariates will be expressed in terms of their mean and standard deviation or median and interquartile range as appropriate. Patients will be divided for seropositive RA and seronegative RA (according to anti-CCP status). The unadjusted comparisons between groups of the covariates and the outcomes will be evaluated using chi² tests for categorical data, while for continuous data, the Student's t-test will be used for normally distributed variables and the Kruskall-Wallis test for non-parametric data.

The effect of biologic treatment response in patients with sero-positive RA will be determined with a multivariate analysis by using a stepwise linear regression model. The response variable is defined as DAS28 and CDAI at last visit. The baseline variables considered demographic data, disease duration (years), methotrexate (yes/no), current steroid therapy (yes/no), baseline DAS28 and CDAI, RF positive (yes/no), anti-CCP (yes/no), and present smoking (yes/no).

The effect of response will be determined by using change from baseline in DAS28 and CDAI at the last visit. A p-value of <0.05 is considered statistically significant, without multiplicity adjustment, for this post-hoc analysis.

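### Background DMARD treatment is only partly controlled: any conventional DMARD is admitted, but only methotrexate yes/no is extracted and modelled

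*Combined protocol and SAP*

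**What the plan says.** On who enters, section 8.2 (Study population) states: "This includes patients who were in monotherapy or in combo-therapy with concomitant conventional DMARDs". No agent is named or excluded. The numbered criteria do not narrow this. Apart from diagnosis and age, section 8.2.1 restricts only earlier biologic use ("Did not receive previous another biological treatment"), and section 8.2.2 excludes earlier biologic use and "Use of etanercept for less than 1 year".

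On what is recorded, section 8.3 lists as background treatment only "current MTX and steroid therapy (yes/no").

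On what is modelled, section 8.6 plans a "multivariate analysis by using a stepwise linear regression model" whose candidates include "methotrexate (yes/no), current steroid therapy (yes/no), baseline DAS28 and CDAI", together with demographics, disease duration, smoking, RF and anti-CCP. It has no term for another conventional DMARD, no indicator of monotherapy versus combination, and no stratified or sensitivity analysis by background DMARD. Section 8.8 names missing data as the only limitation.

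**The concern.** Section 8.2 distinguishes etanercept alone from etanercept with a conventional DMARD, and the chosen covariate cannot reproduce that distinction. The methotrexate-no group mixes true monotherapy with combination therapy based on another agent. The methotrexate-yes group mixes methotrexate alone with methotrexate plus a second agent.

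This matters for the primary objective, the clinical impact of RF and anti-CCP under etanercept. The protocol's background section makes confounding plausible. It links DMARD treatment (there, early initiation) to better outcomes, RF to a more severe course, and anti-CCP positivity to more active disease. One may infer, though the protocol does not say so, that seropositive patients receive more or different DMARDs. If they do, part of the effect of the unrecorded agents would be read as a serostatus difference in response to etanercept. It could hide a real difference, and so appear to support the section 8.2 hypothesis of no difference, or it could create a spurious one. A larger sample would not remove it.

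**Working it through.** The documents state no sample size, effect size or treatment frequency, so there is no planned figure to reproduce. The check has two parts.

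**1. Coding.** Section 8.2 allows four background states, and sections 8.3 and 8.6 give them two codes:

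| Background at etanercept start | Methotrexate code |
|---|---|
| No conventional DMARD | no |
| Other conventional DMARD only | no |
| Methotrexate only | yes |
| Methotrexate plus another | yes |

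No other variable in section 8.3 or 8.6 separates the two states that share a code.

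**2. Size, on assumed inputs.** Take one serostatus indicator in place of the RF and anti-CCP terms, a true serostatus effect of zero, the same methotrexate share in both serostatus groups, and other DMARDs used only by patients not on methotrexate. When the other-DMARD term is left out:

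bias in serostatus coefficient = (share not on methotrexate) × (other-DMARD share among them, seropositive minus seronegative) × (effect of the other DMARD on DAS28)

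Every input below is an assumption.

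| Not on methotrexate | Other DMARD, seropositive v seronegative | Effect (DAS28) | Bias |
|---|---|---|---|
| 0.5 | 30% v 30% | −0.3 or −0.6 | 0 |
| 0.5 | 40% v 20% | −0.3 | 0.5 × 0.20 × (−0.3) = −0.03 |
| 0.5 | 40% v 20% | −0.6 | 0.5 × 0.20 × (−0.6) = −0.06 |
| 0.5 | 60% v 20% | −0.6 | 0.5 × 0.40 × (−0.6) = −0.12 |
| 0.4 | 60% v 40% | −0.4 | 0.4 × 0.20 × (−0.4) = −0.03 |
| 0.5 | 70% v 30% | −0.8 | 0.5 × 0.40 × (−0.8) = −0.16 |

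A negative value means that seropositive patients appear to do better than they do. Least-squares fits to simulated data (70% seropositive) agreed with the formula within about 0.005. Adding an other-DMARD yes/no term returned the serostatus coefficient to zero within 0.003. That recovery follows from the assumed model, in which the added term is the only thing missing. It does not show that the term would remove all confounding in real data.

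The illustration does not cover the merger within the methotrexate-yes group, which would add a similar term if a second agent has a further effect. It also leaves out baseline DAS28 and CDAI, and no size was worked out for CDAI.

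**The case against.** The strongest case against the point has four parts.

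- **Control is not absent.** Section 8.6 offers "methotrexate (yes/no), current steroid therapy (yes/no") and both baseline activity scores to the model. A reader might infer from the coding gap that background treatment is uncontrolled. The documents do not support that; control is partial. Even so, these terms are only candidates, and stepwise selection may drop any of them.
- **Baseline scores may absorb much of the mechanism.** If seropositive disease is treated more intensively because it is more severe, baseline DAS28, CDAI and disease duration capture part of that. For an agent already being taken at baseline, only an effect beyond the one already in the baseline score can bias the result. This stands, and the assumed effects of 0.3 to 0.8 must be read as incremental.
- **No imbalance has been shown.** The documents give no DMARD frequencies by serostatus, and with balanced use the bias is zero. This stands too. Sampling error may also be larger than the bias. With an assumed residual SD of 1.2 and a 70/30 split, the standard error of an unadjusted serostatus difference is 1.2 × √(1/140 + 1/60) = 0.19 at n = 200 and 1.2 × √(1/350 + 1/150) = 0.12 at n = 500. Most of the range lies within one standard error.
- **The methotrexate coefficient is not a target.** If all agents had the same effect and 54% to 61% of methotrexate non-users took another one, that coefficient would keep only about 1 − 0.54 = 46% to 1 − 0.61 = 39% of its true value. A reader might infer that the study fails because it cannot compare monotherapy with combination. Sections 7 and 8.1 set no such objective, and section 8.2 mentions both regimens only to say that both are eligible.

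What remains is the mismatch itself. The plan treats methotrexate as worth adjusting for and gives no reason to treat other conventional DMARDs differently.

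**Conclusion.** The point holds as one of partial control. Eligibility admits any conventional DMARD, the data and model carry methotrexate alone, and no other section makes up for it. Bias in the RF and anti-CCP coefficients needs two conditions: other-DMARD use must differ by serostatus, and it must affect DAS28 or CDAI beyond its effect on baseline. Under the assumed inputs the size runs from 0 to about 0.16 DAS28 units; the true size is unknown and may be zero. The documents do not support a claim that the serostatus comparison is shown to be biased. This is a cheap improvement worth making, not a fault that by itself invalidates the analysis.

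**What to change.** - **Section 8.3:** extract concomitant conventional DMARD at etanercept start as none, methotrexate only, other only, or methotrexate plus other. Two yes/no fields, methotrexate and other conventional DMARD, would also do.
- **Section 8.6:** use this in place of methotrexate (yes/no), and keep it in the model regardless of stepwise selection. Tabulate it by RF and anti-CCP status; that table alone shows whether there is an imbalance to worry about.
- **Section 8.8:** if the registry does not hold the information, state the residual confounding by other conventional DMARDs as a limitation.

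A three-level version that pools methotrexate alone with methotrexate plus another, or a single any-DMARD indicator, would leave some of the merged states merged.

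The cost is one more field and one or two extra degrees of freedom (one for two yes/no terms, two for four categories in place of two), with possible missing values. Section 8.2 says that both regimens are included, but not that the registry stores each agent as a structured field, so availability must be checked. Section 5 records the end of data collection on 01 August 2020 and the final report on 29 June 2021. If the data set is closed, the change therefore means a re-export and re-analysis.

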8.4. Study Size

There is no pre-identified study size sample. All patients that meet the criteria will be entered into the study.

8.5. Data Management

The structured data is exported into an Excel spreadsheet and then transferred to the SPSS (version 23) database for statistical analysis.

8.6. Data Analysis

Categorical covariates will be described by frequency distribution while continuous covariates will be expressed in terms of their mean and standard deviation or median and interquartile range as appropriate. Patients will be divided for seropositive RA and seronegative RA (according to anti-CCP status). The unadjusted comparisons between groups of the covariates and the outcomes will be evaluated using chi² tests for categorical data, while for continuous data, the Student's t-test will be used for normally distributed variables and the Kruskall-Wallis test for non-parametric data.

The effect of biologic treatment response in patients with sero-positive RA will be determined with a multivariate analysis by using a stepwise linear regression model. The response variable is defined as DAS28 and CDAI at last visit. The baseline variables considered demographic data, disease duration (years), methotrexate (yes/no), current steroid therapy (yes/no), baseline DAS28 and CDAI, RF positive (yes/no), anti-CCP (yes/no), and present smoking (yes/no).

The effect of response will be determined by using change from baseline in DAS28 and CDAI at the last visit. A p-value of <0.05 is considered statistically significant, without multiplicity adjustment, for this post-hoc analysis.

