NON-INTERVENTIONAL (NI) STUDY PROTOCOL

Study Information

Title	The impact of RF, and anti-CCP on RA patients in response to Etanercept
Protocol number	B1801417
Protocol version identifier	3.0
Date	27 July 2021
Active substance	etanercept
Medicinal product	etanercept
Research question and objectives	The RF and anti-CCP are found to be positive in 70% and 65% of RA patients respectively. Researchers have found that RF and anti-CCP have an impact on RA response. The objective is to evaluate the impact of RF and ACCP on RA patients in response to Enbrel from the local data.
Author	PPD [REDACTED] – MD, M.Sc. PPD [REDACTED] Pfizer Inc. - Iraq
This document contains confidential information belonging to Pfizer. Except as otherwise agreed to in writing, by accepting or reviewing this document, you agree to hold this information in confidence and not copy or disclose it to others (except where required by applicable law) or use it for unauthorized purposes. In the event of any actual or suspected breach of this obligation, Pfizer must be promptly notified.	

PFIZER CONFIDENTIAL

[figure not shown]
[REDACTED]

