6. RATIONALE AND BACKGROUND

In the past 1–2 decades, treatment paradigms in rheumatoid arthritis (RA) have shifted dramatically from initial treatment with nonsteroidal anti-inflammatory drugs (NSAIDs), followed by cautiously progressive addition of disease-modifying antirheumatic drugs (DMARDs), to the current treatment approach of aggressive initiation of DMARD therapy soon after the diagnosis of RA has been made. This change in RA management results from increasing data supporting improved prognosis and outcomes with the initiation of DMARD therapy early in the course of symptomatic disease.^{1,3}

Rheumatoid factor (RF) has long been a component of the diagnostic criteria for rheumatoid arthritis and although it positive in 70% of RA patients. RF is well studied and its associations with a more severe disease course have been extensively described in Western countries. In more recent years, anti-CCP was positive in 65%-80% of RA patients. The anti-CCP status provides important prognostic information in RA. Also, Rönnelid et al showed that anti-CCP seropositive patients had more active disease during follow-up than seronegative patients.²

Given the optionality of biological treatment for RA patients, identifying a predictor for response will required more attention from rheumatologists for such patients.⁴

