7. RESEARCH QUESTION AND OBJECTIVES

The objective of this study is to evaluate the impact of RF and anti-CCP positivity on RA patients.

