8. RESEARCH METHODS

8.1. Study Design

- **Retrospective analysis** of patients with RA that received etanercept from Baghdad Teaching Hospital (Rheumatology center) from May 2012 until August 2019 (inclusion and exclusion criteria will apply for selecting patients).
- **Primary objective:** Determine the clinical impact of RF and anti-CCP for management (etanercept) in patients with RA compared to negative RF and anti-CCP in RA patients.

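### Section 8.6 groups patients by anti-CCP alone and leaves RF to stepwise selection, so the RF half of the objective may get no estimate and the split isolates neither marker

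*Combined protocol and SAP*

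**What the plan says.** Three places name both markers. Study Information: "The objective is to evaluate the impact of RF and ACCP on RA patients in response to Enbrel from the local data". Section 7: "evaluate the impact of RF and anti-CCP positivity on RA patients". The primary objective in section 8.1 takes RF and anti-CCP together and gives the comparator as "compared to negative RF and anti-CCP in RA patients". The hypothesis in section 8.2 speaks of seropositive and seronegative patients without defining the terms.

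The only definition is in section 8.6: "Patients will be divided for seropositive RA and seronegative RA (according to anti-CCP status". The unadjusted tests follow directly as comparisons between groups. RF then appears among the candidate variables of a stepwise linear regression: "RF positive (yes/no), anti-CCP (yes/no), and present smoking (yes/no". No rule keeps either marker in the model, and no entry or removal criteria are given. The sentence that introduces the regression describes its target as response in seropositive patients. Significance is judged at 0.05, "without multiplicity adjustment, for this post-hoc analysis".

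Both markers are extracted: section 8.3 lists "RF status, anti-CCP status".

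**The concern.** The groups in section 8.6 do not match the objective. Section 8.1 can mean each marker against its own negatives, or double-positive against double-negative. The anti-CCP split delivers only the anti-CCP half of the first and none of the second.

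Two things are at stake. First, RF is half of the objective, yet no step guarantees an estimate for it. Second, the unadjusted seropositive versus seronegative difference has no clean meaning. It compares a group that may be mostly RF-positive with a group that may itself contain RF-positive patients, so a conclusion about RF and anti-CCP, or about anti-CCP alone, could be misread.

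**Working it through.** The plan states no sample size, power or marker cross-table, so there is no figure of its own to reproduce. The check has a textual part and an arithmetic part.

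**1. Is an RF result guaranteed?**
- Unadjusted step: the groups are anti-CCP groups. Comparing covariates between them shows how many seronegative patients are RF-positive, but not the outcome by RF.
- Adjusted step: RF is reported only if it is selected. As an illustration, assume it is retained when |Z| > 1.96. It is then kept with probability 0.05, 0.17, 0.50 and 0.80 for true effects of 0, 1.0, 1.96 and 2.8 standard errors. Once kept, its estimate averages 2.45, 1.41 and 1.13 times the truth for the last three.
- If the model is confined to anti-CCP-positive patients, as its introductory sentence may imply, anti-CCP is constant and RF is estimated only within that group.

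**2. How many seronegative patients are RF-positive?**

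Inputs: RF 70% (Study Information, section 6); anti-CCP 65% (Study Information), while section 6 says "anti-CCP was positive in 65%-80% of RA patients". These describe RA generally, not this cohort.
- Minimum RF+/anti-CCP−: max(0, 0.70 − 0.65) = 0.05 of all patients, or 0.05/0.35 = 14% of the seronegative group.
- Maximum: min(0.70, 0.35) = 0.35 of all patients, or 100% of that group.
- Independence (an assumption): 0.70 × 0.35 = 0.245, or 70% of that group.
- With anti-CCP at 70% or more, the minimum is 0.

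**3. What does the anti-CCP split measure at 70%/65%?**

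Cells (++, RF only, anti-CCP only, −−):
- maximal overlap: 0.65, 0.05, 0, 0.30
- independence: 0.455, 0.245, 0.195, 0.105

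Let each marker add 1 to the effect.
- Maximal overlap: the anti-CCP+ mean is 2.00 and the anti-CCP− mean is 0.05/0.35 = 0.143. The difference is 1.86. That is 1.86 times anti-CCP's own effect of 1, and 1.86/2 = 93% of the double-positive versus double-negative difference.
- Independence: 1 + 0.70 = 1.70 against 0.70. The difference is 1.0, which is 1.0 times anti-CCP's own effect and 50% of the double contrast.

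If instead any positive marker carries the full effect, the share of the double contrast kept is 1 − 0.143 = 86% at maximal overlap and 1 − 0.70 = 30% at independence. If only anti-CCP acts, 100% is kept. If only RF acts, 86% (maximal overlap) to 0% (independence) of a pure RF effect appears as an anti-CCP difference.

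**The case against.** **RF is in the plan.** It is extracted, described and offered to the regression, so a reader who infers that RF is ignored would be wrong. This stands. But being a candidate for selection does not guarantee an estimate.

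**The unadjusted comparisons may cover RF.** The sentence on unadjusted tests mentions covariates and outcomes together, and could loosely mean outcomes across the levels of each covariate. That cannot be excluded. It directly follows the anti-CCP split, however, and names no RF groups. If it was intended, section 8.6 should say so.

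**The bias has no single direction.** A reader might infer that the split pulls the result toward the hypothesis of no difference. The documents do not support that as a general statement. Dilution holds only against double-positive versus double-negative, and only if RF+/anti-CCP− patients share the effect. If section 8.1 means each marker against its own negatives, the anti-CCP split is the intended unadjusted contrast. A positively associated RF acting in the same direction then pushes it away from the null. This objection stands, and the conclusion is stated accordingly.

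**The size is poorly determined.** This also stands. No cross-table is given, the forced minimum disappears once anti-CCP reaches 70%, and independence is an assumption, probably a poor one if the markers are positively associated. It would be wrong to infer that a particular share of this cohort is misclassified.

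**The analysis is post hoc and already reported.** Section 5 lists the final report as issued on 29 June 2021. That limits the remedy to a supplementary analysis or a narrower conclusion. It does not explain why a marker named in the objective has no assured result.

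**Conclusion.** The mismatch is textual and holds without any assumption about prevalence: the objective names RF and anti-CCP, and the groups are formed on anti-CCP alone. Any RF+/anti-CCP− patient is called seronegative, and on the natural reading the plan can finish without an RF estimate, adjusted or unadjusted. The regression's population is also ambiguous.

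The anti-CCP split isolates neither marker. The direction and size of the discrepancy depend on the comparator, the overlap and how the markers act, so the multiples and percentages above illustrate the problem and do not estimate it for this cohort. The 14% minimum applies only at 70%/65%.

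The planned anti-CCP comparison remains valid as an unadjusted description. What the plan does not secure is a conclusion about RF, or one about the two markers jointly. This should be fixed.

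**What to change.** In section 8.6:

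- (a) State that the adjusted model is fitted to all patients, force in both RF and anti-CCP, and report both coefficients with confidence intervals whatever their significance.
- (b) Keep the anti-CCP split. Add unadjusted RF+ versus RF− and double-positive versus double-negative estimates with confidence intervals, and describe the two single-positive groups.
- (c) Label the additions supplementary and post hoc, given the report date in section 5.

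Otherwise, restate the objective, hypothesis and conclusions as anti-CCP only, which needs no reanalysis.

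The work is a change of wording, one derived variable and a re-run. The statistical costs at 70%/65%, assuming equal variances, are:

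- **Double contrast.** Its standard error relative to the planned split is √[(1/0.65 + 1/0.30)/(1/0.65 + 1/0.35)] = 1.05 at maximal overlap and √[(1/0.455 + 1/0.105)/(1/0.65 + 1/0.35)] = 1.63 at independence. The double-negative group is 30% down to 10.5% of patients, against 35% in the planned reference group.
- **RF split.** √[(1/0.70 + 1/0.30)/(1/0.65 + 1/0.35)] = 1.04.
- **Forced coefficients.** At maximal overlap the correlation is (0.65 − 0.455)/√(0.70 × 0.30 × 0.65 × 0.35) = 0.892. The variance inflation is 1/(1 − 0.892²) = 4.9, so standard errors are about 2.2 times as large; there is no inflation at independence. If the markers agree in every patient, their effects cannot be separated.
- **Multiplicity.** If the additions were tested, the unadjusted outcome tests on DAS28 and CDAI would rise from 2 to 6, or from 4 to 12 if last-visit value and change are both tested. Reporting the additions as estimates with intervals avoids presenting them as further significance tests.

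### Section 8.6 describes its only adjusted model as one for seropositive patients yet lists anti-CCP as a covariate, and even an all-patient stepwise model need not yield an adjusted serostatus estimate

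*Combined protocol and SAP*

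**What the plan says.** All statements below are in the combined protocol and SAP.

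- **Groups (Section 8.6).** "Patients will be divided for seropositive RA and seronegative RA (according to anti-CCP status"). Anti-CCP alone decides the group.
- **Between-group tests (Section 8.6).** "The unadjusted comparisons between groups of the covariates and the outcomes will be evaluated using chi² tests for categorical data", with a t-test or a rank-based test for continuous data. No adjustment is attached to these.
- **Adjusted model (Section 8.6).** "The effect of biologic treatment response in patients with sero-positive RA will be determined with a multivariate analysis". The method named is linear regression with stepwise selection. The outcome is given as follows: "The response variable is defined as DAS28 and CDAI at last visit".
- **Candidate covariates (Section 8.6).** These include "RF positive (yes/no), anti-CCP (yes/no), and present smoking (yes/no"), alongside demographics, disease duration, methotrexate, steroids and the baseline scores.
- **Objective (Section 8.1).** The clinical impact of RF and anti-CCP under etanercept, "compared to negative RF and anti-CCP in RA patients". The hypothesis in Section 8.2 is likewise framed as seropositive against seronegative.
- **Study size (Section 8.4).** No sample size is set, and every patient meeting the criteria enters the study.

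No other section states the population of the regression or gives an adjusted comparison between the serogroups.

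**The concern.** The sentence introducing the regression names one serogroup, while its covariate list needs both. Two analysts working from Section 8.6 could fit different populations and report different answers to the primary question.

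This matters because the groups are not randomised. Section 6 itself says that RF is associated with a more severe disease course and that anti-CCP-positive patients had more active disease during follow-up. Confounding by severity is therefore part of the protocol's own premise, and the regression is the only planned control for it. Section 8.8 mentions only missing data as a limitation.

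A second weakness survives on either reading. The model is stepwise, and no coefficient is named as the answer to the objective. The marker terms are candidates like any other and may not be in the final model.

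**Working it through.** The plan gives no sample size, power or effect size, so there is no stated figure to reproduce. The question is which coefficients can be estimated under each reading.

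**1. Model.** A reduced form is enough to show the point:

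outcome = b0 + b1 × baseline score + b2 × RF + b3 × anti-CCP + error

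The coefficient b3 is the adjusted seropositive-minus-seronegative difference, because Section 8.6 defines the groups by anti-CCP.

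**2. Seropositive-only reading.** Every patient has anti-CCP = 1, so the model becomes (b0 + b3) + b1 × baseline score + b2 × RF + error. Only the sum b0 + b3 can be estimated. Patients negative for both markers, the comparator suggested by Section 8.1, are all outside this set. The coefficient b2 can still be estimated, but it compares RF-positive with RF-negative patients among the anti-CCP-positive only.

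**3. Numerical check.** One data set was simulated under assumptions that are not in the documents: N = 300, 65% anti-CCP positive, and RF positive in 85% of anti-CCP-positive and 42% of anti-CCP-negative patients.

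| Patients in model | Rank of design matrix | Anti-CCP coefficient |
|---|---|---|
| All 300 | 4 of 4 | can be estimated |
| 198 anti-CCP positive | 3 of 4 (anti-CCP variance 0) | cannot be estimated |

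RF variance in the subset was 0.12, so the RF term survives there.

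**4. Share left out under the seropositive-only reading.** Section 6 gives background anti-CCP positivity of 65-80%. Then 1 − 0.80 = 0.20 and 1 − 0.65 = 0.35, that is 20-35%. This is an assumption carried over from RA patients in general. The share among first-biologic etanercept users in this registry is not given.

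**5. All-patient reading with selection.** The coefficient b3 can be estimated, but only if the term is selected. As an illustration, 1,000 data sets were simulated per setting, with residual SD 1.1, a true adjusted DAS28 difference of 0.3, 65% positivity, and anti-CCP entering after baseline if p < 0.05. The plan states neither its entry and removal thresholds nor N, so these are assumptions too, and this is a single entry step, not the full stepwise procedure.

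| N | Anti-CCP enters, true difference 0.3 | Anti-CCP enters, no difference |
|---|---|---|
| 100 | 25% | 5% |
| 300 | 61% | 5% |
| 600 | 88% | 6% |

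When the term does not enter, there is no adjusted difference or interval to report. With no true difference, which is what Section 8.2 hypothesises, that happens in about 95% of runs.

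**The case against.** The strongest reply is that the plan never says the regression is fitted only to seropositive patients. The sentence describes, clumsily, what is to be learned and does not define an analysis set. The context favours an all-patient model: "RF positive (yes/no), anti-CCP (yes/no") makes sense as a covariate list only with both serogroups present, the model follows directly after the tests labelled unadjusted and reads as their adjusted counterpart, the objective and hypothesis compare positive with negative, and Section 8.4 takes in all eligible patients. An analyst who restricted the data would also find at once that a listed covariate could not be estimated.

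Most of this stands. A reader might infer that the plan specifies a seropositive-only model and so deliberately leaves its primary comparison unadjusted. The documents do not support that; the likelier intent is the opposite. What remains is that the wording contradicts itself and no other section settles it.

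It can also be said that stepwise selection is a separate matter from the model population. It belongs here because correcting the population alone would still not guarantee the adjusted estimate that the objective needs.

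**Conclusion.** The point holds as an internal contradiction in Section 8.6, together with a selection rule that can remove the terms of interest. It should be corrected. The result for the seropositive-only reading follows from the plan's own definition and needs no assumption: the anti-CCP contrast cannot be estimated, and only an RF contrast within anti-CCP-positive patients is left. The 20-35% share outside the model rests on the background positivity in Section 6. The entry rates under selection are illustrative and depend on the assumed N, effect and residual SD.

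A reader might also want to attach a false-positive rate to the unadjusted comparison. The documents give neither the cohort size nor the baseline difference between serogroups, so no such figure is claimed. Nor do they show which population was actually analysed.

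**What to change.** Replace the sentence introducing the regression in Section 8.6 with wording to this effect: *A linear regression is fitted to all eligible patients, seropositive and seronegative. Anti-CCP (positive versus negative) and RF (positive versus negative) are kept in the model whatever their p-value. Their adjusted differences, with 95% confidence intervals, are the answer to the primary objective. Any model restricted to seropositive patients is secondary.*

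Section 5 gives 29 June 2021 as the actual date of the final report, before protocol version 3.0 of 27 July 2021. The sponsor should therefore also state which population was modelled and whether both marker terms were in the final model.

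The cost depends on that answer. If all patients were modelled and both terms stayed in, it is one or two sentences of text. If the model was seropositive-only, or selection removed either term, the regression has to be rerun and the report revised. No new data are needed in either case, since RF, anti-CCP and the baseline scores are already among the items listed in Section 8.3.
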